Our goals in this study are:

- 1. To evaluate the effectiveness of surgical decompression in migraine headaches prospectively, using validated instruments, and to compare it to the effectiveness of a botulinum toxin injection protocol
 - a. Our hypothesis is that migraine surgery decreases the frequency and severity of migraine headaches significantly, as measured by

validated questionnaires, and that the reduction is greater and more sustainable than that seen with a botulinum toxin injection protocol

- 2. To determine which types of migraine headaches benefit most from surgical decompression and/or botulinum toxin injection
- 3. To identify prognostic factors for the success or failure of surgical decompression in migraine headache
 - a. These have been demonstrated in a previous study,⁹ but have not evaluated in a multi-center fashion.
- 4. To compare the long-term direct and indirect costs in patients with migraine headaches undergoing botulinum toxin A injections versus surgical decompression
 - a. We hypothesize that, over the long-term, surgical decompression is more cost-efficient than a botulinum toxin injection protocol

III. Procedures

a. Research design

This is a **prospective, multi-center** evaluation of the short, medium and long-term efficacy of surgical decompression in migraine headaches, comparing it to the efficacy of a botulinum toxin injection protocol.

b. Sample

Inclusion criteria:

-Patients with migraines related to a trigger site at the location of a branch of a cranial nerve (frontal, temporal, occipital)

-Patients with chronic migraine (≥15 days per month) as dictated by the FDA indication for botulinum, and as diagnosed by a board-certified neurologist

Exclusion criteria:

-Patients deemed by the senior author or the neurologist to not have migraine headaches, but an alternative diagnosis

-Patients with systemic conditions that make them poor candidates for surgery (coronary artery disease, uncontrolled diabetes mellitus, etc...)

-Patients with migraines related to inferior turbinate hypertrophy or septal deviation -Patients with a frontal, temporal or occipital trigger point who do not respond to a diagnostic botulinum toxin injection

-Hypersensitivity to any botulinum toxin preparation or to any of the components in the formulation

-Infection at the proposed injection site for botulinum

Sample size (power analysis)

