Since there are several endpoints in this study, the required sample size can be calculated in several ways:

-Using efficacy as an endpoint:

In Janis *et al*,⁶ patients undergoing botulinum toxin injections had an average improvement in their Migraine Headache Index of 87.5%. In comparison, patients undergoing surgery had an average improvement of 96.6%.

Assuming a standard deviation of 20%, an alpha error of 5%, and a power of 80%, the required sample size using this method is **30 patients in each group**.

-Using total cost of treatment as an endpoint:

Assuming an average injection volume of 75 Units of botulinum toxin every 3 months, and assuming a cost of \$12-15 per Unit, the estimated cost of a botulinum toxin A injection protocol over one year is \$3,600-\$4,500.

In comparison, the estimated cost of surgery (including facility fee, surgeon fee, preoperative testing and follow-up) is \$8,378.¹⁰

Therefore, in order to demonstrate a financial superiority of surgery versus botulinum toxin, the patients would need to be follow-up for 1.9 to 2.3 years. Assuming a study follow-up of 2.5 years, and average costs of botulinum and surgery of $$10,125 \pm $2,000$ and $$8,378 \pm $2,000$, respectively, and assuming an alpha error of 5%, a power of 80%, the required sample size using this method is **16 patients in each group**.

-Using treatment success by trigger site as an endpoint:

According to Larson *et al*,⁹ the success rates for surgery by trigger site were as follows: Frontal 83.3%, temporal 75.8%, and occipital 45.5%. In order to discern a difference between the outcomes for the two sites with the closest outcomes (frontal and temporal), and assuming a standard deviation of 10%, an alpha error of 5%, and a power of 80%, the required sample size using this method is **14 patients in each group**.

Looking at the three methods above, keeping the method yielding the highest required number of participants, and accounting for any participant drop-out, we will seek to enroll **50 patients in each group.**

c. Detailed study procedures

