A neurologist will evaluate patients presenting for evaluation for treatment of migraine headaches, for confirmation of the diagnosis of migraine. The type of migraine that they suffer from will be recorded. If the diagnosis of migraine is confirmed, they will sign an informed consent form, and they will be asked to complete a daily headache diary, and keep track of their 1) daily use of medications for migraines, 2) physician visits for migraines, 3) ER visits for migraines, 4) days of work lost due to migraines, 5) other costs directly related to migraines for 2 months. They will also be asked to

complete three questionnaires: the Migraine Work and Productivity Loss Questionnaire (MWPLQ),¹¹ the Migraine Disability Assessment questionnaire (MIDAS)¹² and the Migraine-Specific Quality of Life questionnaire (MSQ) at the time of enrollment.

All patients will undergo a history and physical examination, including an intranasal examination. This will include determination of the possible trigger site: frontal, temporal, occipital, and inferior turbinate/septum. The trigger site can be determined using a combination of three methods: 1) Physical examination, 2) Diagnostic botulinum toxin injection into a specific trigger point, and 3) Nerve block using a local anesthetic injected into a specific trigger point in patients having active symptoms.

The patients will be asked whether they prefer to undergo surgical decompression or a botulinum toxin protocol, and their preference will be recorded.

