50 patients who prefer surgery, and who satisfy the inclusion and exclusion criteria, will be included in the study as **Group A**. The location of the trigger site(s) will be determined based on history, physical examination, a diagnostic botulinum toxin injection and/or a nerve block. If those patients are found to have a trigger site that responds to botulinum injection, they will undergo surgical decompression of their trigger site, as described in Janis *et al*⁶ and Guyuron *et al*.⁷ Those patients will be followed postoperatively. They will be asked to continue tracking their 1) daily use of medications for migraines, 2) physician visits for migraines, 3) ER visits for migraines, 4) days of work lost due to migraines, and 5) other costs directly related to migraines for 2 months. At 1 year, 2 years and 2.5 years postoperatively, they will be asked to fill the Migraine Work and Productivity Loss Questionnaire (MWPLQ), the Migraine Disability Assessment questionnaire (MIDAS) and the Migraine-Specific Quality of Life questionnaire (MSQ) again. They will also be examined by a board-certified neurologist at 1 year postoperatively.

A separate sample of 50 patients from the pool of patients undergoing the botulinum toxin injection protocol will be selected (Group B). Those patients will be matched to the individual patients in group A based on gender, age (in 5 year intervals), migraine severity (based on the Migraine Disability Assessment questionnaire, 5 –point intervals) and trigger site (pair-matching). For example, for a patient in Group A who is a 47 year-old woman with temporal migraines and a MIDAS severity score of 14, a patient on the botulinum injection protocol will be included in Group B is she is a 45 to 50 year old female with temporal migraines and a MIDAS severity score of 10 to 15.

The patients in group B will receive the botulinum injection protocol, and will continue to track their 1) daily use of medications for migraines, 2) physician visits for migraines, 3) ER visits for migraines, 4) days of work lost due to migraines, and 5) other costs directly related to migraines for 2 months. At 1 year, 2 years and 2.5 years after the start of the protocol, they will be asked to fill the Migraine Work and Productivity Loss Questionnaire (MWPLQ), the Migraine Disability Assessment questionnaire (MIDAS)

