and the Migraine-Specific Quality of Life questionnaire (MSQ). They will also be examined by a board-certified neurologist at 1 year postoperatively.

The Botox injections and the surgeries are being done as part of the routine clinical care for the patients enrolled in the study. The only procedures being done solely for research purposes are having the patients fill out the surveys and diaries.

d. Measurements

The measurements will include

- 1) Number of migraine headaches per 30 days
- 2) Cost of migraine-related medications, physician visits, ER visits
- 3) Cost of days of work lost due to migraine as calculated from the Migraine Work and Productivity Loss Questionnaire (MWPLQ)
- Score on the Migraine Disability Assessment Questionnaire (MIDAS) (0-21)
- 5) Scores on the emotional, restrictive and preventive portions of the Migraine-Specific Quality of Life questionnaire (MSQ)

The following comparisons will be made for the above measurements:

-Within Group A, compare all measurements before surgery to 1 year, 2 years and 2.5 years after surgery, using a t-test

-Within Group B, compare all measurements before start of injection protocol to 1 year, 2 years and 2.5 years after injection protocol, using a t-test

-Compare all measurements between Group A and Group B using a paired t-test analysis

e. Internal validity

The study avoids confounding by virtue of the matched-pair analysis. The study avoids recall bias by having the patients fill-out the questionnaires preoperatively and postoperatively, rather than having them retrospectively assess their improvement after surgery.

Blinding is very difficult in such a study. In order to avoid experimenter bias, all assessment will be made by the patients themselves, without influence by the experimenters.

The main threat to internal validity is the possible placebo effect inherent to migraine headache treatments. This may threaten the validity of the data on differences in clinical outcomes between the two groups. It will not threaten the validity of the data on financial cost

f. External validity

Because this is a multi-center trial that includes different patient populations treated by different clinicians, this study is generalizable to the general population of patients with migraines in the United States.

g. Data analysis

Group B will be selected by matching individual participants to members of Group A based on gender, age, migraine severity and migraine location.

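### The 2.5-year cost comparison has no named place for surgery cost, no described direct-cost collection at 1, 2 or 2.5 years, and no cost outcome in the SAP

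*Protocol*

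**What the plan says.** Protocol II, goal 4 is "To compare the long-term direct and indirect costs in patients with migraine headaches undergoing botulinum toxin A injections versus surgical decompression", with the hypothesis that surgery is more cost-efficient over the long term.

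Protocol III.b sizes a total-cost endpoint. Botulinum is costed at 75 units every 3 months at $12-15 per unit. Surgery is costed at $8,378, "including facility fee, surgeon fee, preoperative testing and follow-up". To show a financial advantage for surgery, "the patients would need to be follow-up for 1.9 to 2.3 years". The calculation begins "Assuming a study follow-up of 2.5 years, and average costs of botulinum and surgery of" and uses $10,125 and $8,378, each with SD $2,000, to reach 16 per group.

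Protocol III.c describes a cost log three times: at enrolment ("other costs directly related to migraines for 2 months. They will also be asked to"), after surgery in Group A ("other costs directly related to migraines for 2 months. At 1 year, 2 years and 2.5 years postoperatively") and in Group B ("other costs directly related to migraines for 2 months. At 1 year, 2 years and 2.5 years after the start of the protocol"). At the three late times it lists only the MWPLQ, MIDAS and MSQ, and a neurologist examination at 1 year. It adds: "The Botox injections and the surgeries are being done as part of the routine" clinical care, with surveys and diaries as the only research procedures.

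Protocol III.d, measurement 2, is the cost of medications, physician visits and ER visits for migraine. Measurement 3 is work-loss cost from the MWPLQ. III.d and III.g compare the measurements before treatment with 1, 2 and 2.5 years, and between groups.

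The SAP models six outcomes: MHI, three MIDAS scores, an MSQ sum and an MWPLQ total. None is a cost.

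**The concern.** A long-term cost comparison needs each treatment's cost recorded over the full horizon and an analysis that uses it. Here the plan states the objective, the horizon and the assumed difference, but the steps from there to data and analysis are incomplete. Surgery cost is half of the contrast and has no named measurement. Botulinum cost has one only by interpretation. The t-tests at 1, 2 and 2.5 years include direct cost, but no collection of direct cost at those times is described. The SAP then drops cost altogether.

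This matters because the plan leans on cost. III.e accepts that a placebo effect may threaten the clinical comparison and says that it will not threaten the cost data. A cost result that omits the surgery itself would also err in the direction of the plan's hypothesis if the toxin were counted as a medication.

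**Working it through.** **1. Reproduce the plan's cost figures (III.b).**
- One session: 75 × $12 = $900 to 75 × $15 = $1,125.
- One year, 4 sessions: $3,600 to $4,500, as stated.
- Break-even: 8,378 / 4,500 = 1.86 years to 8,378 / 3,600 = 2.33 years, matching the stated 1.9 to 2.3.
- 2.5 years: 30 / 3 = 10 sessions, $9,000 to $11,250, midpoint $10,125, as stated.
- Sample size: n = 2 × [SD × (z_α + z_β) / Δ]², with Δ = 10,125 − 8,378 = $1,747 and SD = $2,000. One-sided 5%: 2 × [2,000 × (1.645 + 0.842) / 1,747]² = 16.2, so 17. Two-sided: 2 × [2,000 × (1.960 + 0.842) / 1,747]² = 20.6, so 21. The stated 16 is therefore close to a one-sided calculation. That is a separate matter and is not relied on here.

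**2. What the assumed difference consists of.** $1,747 is toxin cost (units times price) minus surgery cost, and nothing else. Across the stated prices it runs from 9,000 − 8,378 = $622 to 11,250 − 8,378 = $2,872.

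**3. What measurement 2 would return, using the plan's own means.**

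| Reading of measurement 2 | Botulinum | Surgery | Difference |
|---|---|---|---|
| Plan's assumption | $10,125 | $8,378 | $1,747 |
| Toxin counted as a medication, surgery not named | $10,125 | $0 | $10,125 |
| Neither counted | $0 | $0 | $0 |

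Row 2 also supposes that toxin use is recorded through 2.5 years. Part of the $8,378 (follow-up, perhaps preoperative testing) might enter as physician visits. The documents do not split the figure, so $8,378 is the most that could be missed per surgical patient.

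**4. What is collected late.** The post-treatment sentence can be read in two ways.
- The 2 months apply to the whole list. The enrolment log has the same wording and is plainly a 2-month log, so this is the more natural reading. One log then covers 2 / 30 = 7% of the 2.5 years. With sessions 3 months apart it can contain at most 1 of about 10.
- The 2 months limit only item 5 (other costs), and tracking of items 1 to 4 is open-ended.

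On either reading, no direct-cost collection is described at 1, 2 or 2.5 years, and surgery is still not named.

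**5. What treatment costs from records could show.** Inputs: SD $2,000 per group (III.b), pair correlation 0 (assumed), two-sided 5%. SD of the paired difference = 2,000 × √2 = $2,828.

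| Complete pairs | SE | t | 95% half-width | Power for $1,747 | Power for $622 |
|---|---|---|---|---|---|
| 50 | 2,828/√50 = $400 | 2.010 | $804 | 99% | 33% |
| 30 (illustrative) | 2,828/√30 = $516 | 2.045 | $1,056 | 90% | 21% |

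The 30-pair row is shown because III.b sets 50 per group partly to allow for drop-out. A positive pair correlation would help: at an assumed 0.5 with 50 pairs, the half-width is $568 and power for $622 is 58%.

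**The case against.** The best reply is that this is abbreviated text and not a missing design. The comparison of all measurements at the late times presupposes late cost data. The post-treatment list also fails to repeat the daily headache diary, although headache frequency is to be compared at the same times, so silence is weak evidence that nothing was planned. The list of measurements is not expressly exhaustive. The plan's botulinum figure is purely drug cost, so it fits under migraine medications. Both treatments are routine care, so billing or treatment records may exist.

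Much of this stands, and it rules out three stronger inferences.
- A reader might infer that both treatment costs are absent from the measurements. The text supports that clearly only for surgery.
- A reader might infer that direct costs are observed for just 2 of 30 months. That depends on the more natural of two readings.
- A reader might infer that the cost objective cannot be answered at all. An intended but unwritten repeat of the log cannot be excluded, records may hold the procedure costs, and indirect cost has a late source in the MWPLQ.

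The reply does not supply a measurement for surgery cost, a written late collection of direct costs, a named record source, or a cost analysis in the SAP. Those gaps remain on every reading.

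**Conclusion.** The point holds for the direct-cost part of goal 4. As written, the comparison would leave out surgery cost, up to $8,378 per surgical patient on the plan's figure, against an assumed difference of $1,747. It could not soundly answer that part of the goal. The timing of the other direct costs is unclear, and the SAP analyses no cost.

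The effect is confined to this goal. Indirect cost and the clinical outcomes are untouched. Enrolment is also unaffected, because the efficacy calculation (30 per group, raised to 50) sets it. The conclusion about surgery cost and the SAP does not depend on how the 2-month wording is read; the 7% coverage figure does. The precision figures rest on the plan's SD, an assumed pair correlation of 0 and the stated number of complete pairs. They say what a repaired analysis could show and do not measure the defect. Worth correcting, at moderate priority.

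**What to change.** 1. Add to measurement 2 each patient's surgery cost and the cost of every botulinum session through 2.5 years, abstracted from routine treatment records. State how follow-up visits are counted once, since the $8,378 already includes follow-up and measurement 2 also counts physician visits.
2. Add to the SAP the between-group difference in arithmetic mean 2.5-year treatment cost, with a 95% CI.
3. State when the post-treatment 2-month log falls. Where later non-procedure costs were not collected, report them as a projection, and restate goal 4 and the 2.5-year cost statement in III.b to match.

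The cost is abstraction for 100 patients (50 surgeries and 50 × 10 = 500 sessions), a short amendment to both documents, and a more modest cost claim. Abstraction may still be possible if follow-up has closed, as the SAP's past tense may suggest. Even with complete records, a true difference near $622 would probably not be shown.

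Repeating the 2-month log before each late assessment is optional and only possible while follow-up is open. It would add up to 3 × 100 = 300 diary periods and still leave 30 − 8 = 22 of 30 months extrapolated, so the fix does not depend on it.

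### Group B is matched on fixed 5-year and 5-point bands with no rule for edges, several trigger sites or unmatched patients, and 50 pairs are unlikely unless the botulinum pool is large

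*Protocol*

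**What the plan says.** Protocol III.c (Detailed study procedures) takes Group B from existing botulinum patients: "A separate sample of 50 patients from the pool of patients undergoing the botulinum toxin injection protocol will be selected (Group B"). No size is given for that pool. The rule is "Those patients will be matched to the individual patients in group A based on gender, age (in 5 year intervals), migraine severity", the last item being "based on the Migraine Disability Assessment questionnaire, 5 –point intervals) and trigger site (pair-matching").

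The example shows how the bands work. It runs: "for a patient in Group A who is a 47 year-old woman with temporal migraines and a MIDAS severity score of 14"; a botulinum patient qualifies if "she is a 45 to 50 year old female with temporal migraines and a MIDAS severity score of 10 to 15". The windows are fixed, not centred on 47 and 14, and both ends are included.

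Protocol III.g (Data analysis) repeats the factors without widths: "Group B will be selected by matching individual participants to members of Group A based on gender, age, migraine severity and migraine location". Sections III.d and III.g compare the groups by paired t-test, and III.e (Internal validity) credits the matched pairs with removing confounding. The SAP (Data Analysis) mentions neither matching nor pairs. It specifies linear mixed models with a patient random effect, treatment, time and their interaction.

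**The concern.** Treatment follows patient preference, so the matched pairs are the protocol's only stated protection against confounding. Three features weaken it.

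- **Fixed bands do not track closeness.** A partner one unit away can be refused while one several units away is accepted.
- **The rule is incomplete.** In the example, 50 years and 15 points each fall in two adjacent bands. III.c allows a patient to have more than one trigger site, but the rule treats site as a single label. Nothing says what happens to a Group A patient for whom no partner exists.
- **Feasibility is not examined.** Each pair must agree on four factors at once, and the documents do not show that the pool can supply 50 such pairs.

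If pairs run short, the paired t-test loses the unpartnered Group A patients. Those who remain are the ones with common profiles.

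**Working it through.** **1. The plan's own figure.** The sample-size section (III.b) uses improvements of 96.6% and 87.5% (difference 9.1), SD 20, alpha 5% and power 80%, and states 30 per group. In paired form, n = (SD × (z_alpha + z_beta) / difference)²:

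- one-sided: (20 × (1.645 + 0.842) / 9.1)² = 29.9, so 30;
- two-sided: (20 × (1.960 + 0.842) / 9.1)² = 37.9, so 38.

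The 30 is therefore reproduced as a one-sided paired calculation. The step to 50 equals 30 / (1 − 0.40), but no dropout rate is stated. For this point, 30 is the plan's requirement before dropout and 50 is the enrolment target.

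**2. How the bands behave.** Against the example patient (47 years, score 14), a same-sex, same-site patient aged 50 scoring 10 is accepted (3 years and 4 points apart). One aged 47 scoring 16 is refused (0 years and 2 points apart). On a single factor, candidates 1, 2, 3 and 4 units away are refused 20%, 40%, 60% and 80% of the time with disjoint bands, and 10%, 30%, 50% and 70% with inclusive ones. A gap of 5 is possible only under the inclusive reading, and only between a band's two end values (45 with 50).

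**3. Expected pairs.** None of the following inputs is in the documents except the MIDAS range (III.d: "Score on the Migraine Disability Assessment Questionnaire (MIDAS) (0-21")). Assumed: both groups from the same population, 85% women, age mean 45 SD 12, MIDAS uniform on 0-21, three equally common sites. Each simulated trial draws 50 Group A patients and a pool, then forms the largest possible number of 1:1 pairs, exact on gender and site. Inclusive means that the partner may fall anywhere in the Group A patient's closed band. The gap is the average of the age difference (years) and the MIDAS difference (points). For the bands it assumes that any eligible partner may be taken, because the protocol gives no rule for choosing among several.

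| Rule | Age × score values admitted | Pairs, pool 100 / 200 / 400 | Mean gap |
|---|---|---|---|
| Disjoint bands | 5 × 5 = 25 | 19 / 29 / 39 | |
| Within 2 | 5 × 5 = 25 | 20 / 31 / 40 | |
| Inclusive bands (example) | 6 × 6 = 36 | 24 / 34 / 42 | about 1.75 |
| Nearest within 3 | 7 × 7 = 49 | 29 / 39 / 45 | 1.45 / 1.22 / 0.94 |
| Nearest within 5 | 11 × 11 = 121 | 40 / 45 / 48 | 1.98 / 1.48 / 1.09 |

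If an edge value may count in both of its bands, the yield rises to 26.5 / 37.3 / 43.8. The unresolved edge rule alone therefore moves the result by about 5 to 8 pairs.

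**4. Sensitivity (inclusive bands, sites at 40/30/30% where there are three).**

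- MIDAS clustered high (mean 16, SD 4): 28.5 pairs at a pool of 100, 37.7 at 200, 45 at 500.
- Seven site sets (2³ − 1 combinations of three sites): 14, 23 and 36 pairs.
- A wider MIDAS scale (mean 60, SD 42): 7, 13 and 24.5 pairs.
- All 50 pairs: probability about zero in every setting up to a pool of 500. With uniform MIDAS and three sites it is 7% at 1,000 and 37% at 2,000.

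**5. Attrition.** A pair is lost if either member leaves. If each patient is lost independently with probability 10%, 0.9² = 81% of pairs survive, and 24 / 34 / 42 become about 19 / 28 / 34. At 20%, 0.8² = 64% survive, giving about 15 / 22 / 27. Both rates are assumptions.

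**The case against.** The strongest reply is that the pool is unknown. The injections are routine care at a multi-center study, and nothing limits the pool to a few hundred. That stands: a reader might infer that 50 pairs cannot be found, but the documents support only a statement conditional on pool size and patient mix.

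A second reply is that the bands are not to blame for the shortage. This also stands. A centred window of equal width (within 2) yields about as few pairs as disjoint bands. The scarcity comes from narrow matching on four factors.

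Third, the gain from distance matching is partly loosening. A limit of 5 admits 121 age-score combinations against 36. That is fair. A limit of 3 is a smaller widening (49 against 36) and gives more pairs with a smaller mean gap. Some of that closeness comes simply from choosing the nearest partner, which could also be done inside bands.

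Fourth, a reader might infer that a shortfall from 50 leaves the trial below its own required size. The requirement before dropout is 30, and inclusive-band yields at pools of 200 and 400 exceed it. Whether they still do after dropout depends on a rate the plan does not give.

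Finally, the SAP's mixed model does not drop unpaired patients. That is correct, so the loss arises only under the paired t-test. But the mixed model contains none of the matching variables, so for patients without a partner it does not replace the control for confounding that the protocol attributes to pairing.

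**Conclusion.** The concern holds as a weakness of method and specification. The fixed bands are a poor measure of closeness. The edge rule, the multi-site rule and the fallback for unmatched patients are missing.

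Under the stated assumptions, pools of 100, 200 and 400 give about 24, 34 and 42 pairs with the example's inclusive bands, and 19, 29 and 39 with disjoint bands. All 50 are unlikely unless the pool is much larger than the trial. These figures depend on assumed distributions and on both groups coming from one population; systematic differences between patients who choose surgery and those who choose injections would tend to lower them.

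The documents do not show that 50 pairs are unattainable, that band edges cause the shortage, that partners 5 apart are accepted under every reading, or that unpartnered patients vanish from every analysis. The point deserves correction but does not by itself invalidate the comparison.

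**What to change.** 1. State the expected size of the botulinum pool and the number of pairs it should supply.
2. Replace the bands with optimal nearest-distance matching on baseline age and MIDAS within a declared maximum gap, exact on gender and on the set of trigger sites. Use baseline data only, and complete the matching before any outcome is seen. In these simulations a maximum of 3 gives more and closer pairs than the inclusive bands. A maximum of 5 gives still more pairs, but in a small pool the mean gap is slightly larger (2.0 against 1.75 at a pool of 100).
3. Say what happens to Group A patients without a partner. Analyse all patients in both groups, partnered or not, in the SAP's mixed model, adding age, gender, baseline MIDAS and trigger site as covariates. For the MIDAS outcomes, state whether the baseline score enters as a covariate or as a repeated response, so that it is not used twice.
4. Make the between-group analysis in the protocol agree with the SAP.

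The cost is protocol and SAP wording plus a standard matching routine, with no new data. Part of the gain in pairs is bought with a wider tolerance, so the maximum gap must be declared. The covariates use a few degrees of freedom.
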